3.9.7 Surgery

Susceptibility to bleeding has been observed with the first generation BTK inhibitor, ibrutinib (IMBRUVICA prescribing information). As a precaution, it is suggested that acalabrutinib be withheld for 3 days before and for 3 days after any major surgical procedure.

3.9.8 Reproductive Toxicity

Developmental and reproductive toxicology studies in rats have not identified acalabrutinib-related toxicities for fertility, reproductive success, embryofetal development or embryofetal survival. In rabbits, at dose levels that resulted in maternal toxicities, skeletal variations were associated with reductions in fetal weights. Effects on parturition and post-natal development are pending. For additional details, refer to the Acalabrutinib Investigator Brochure. *Women of childbearing potential (WOCBP)* subjects who are sexually active must use highly effective methods of contraception during *treatment* and for 2 days after the last dose of acalabrutinib. *For male subjects with a pregnant or non-pregnant WOCBP partner, no contraception measures are required. WOCBP are women who are fertile following menarche and until becoming postmenopausal unless permanently sterile; permanent sterilization methods include hysterectomy, bilateral salpingectomy, and bilateral oophorectomy.*

Women are considered to be of non-reproductive potential if they meet any of the below criteria:

- *Postmenopausal, defined as at least 12 months with no menses without an alternative medical cause; in women <45 years of age. A high follicle-stimulating hormone (FSH) level in the postmenopausal range may be used to confirm a postmenopausal state in women not using hormonal contraception or hormonal replacement therapy. In the absence of 12 months of amenorrhea, a single FSH measurement is insufficient.*

- *Have had a hysterectomy and/or bilateral oophorectomy, bilateral salpingectomy, or bilateral tubal ligation/occlusion, at least 6 weeks before Screening*
- *Have a congenital or acquired condition that prevents childbearing*

Men are considered to be of non-reproductive potential if they are permanently sterile due to bilateral orchidectomy.

Highly effective methods of contraception (to be used during heterosexual activity) are defined as methods that can achieve a failure rate of <1% per year when used consistently and correctly. Such methods include:

- *Combined (estrogen- and progestogen-containing) hormonal contraception associated with inhibition of ovulation, which may be oral, intravaginal, or transdermal*
- *Progesterone-only hormonal contraceptives associated with inhibition of ovulation, which may be oral, injectable, or implantable*
- *Intrauterine devices (IUD) or intrauterine hormone-releasing system (IUS)*
- *Bilateral tubal occlusion*
- *Vasectomy of a female subject's partner (with medical assessment and confirmation of vasectomy surgical success)*
- *Sexual abstinence (only if refraining from heterosexual intercourse during the entire period of risk associated with the study treatments)*

Hormonal contraception may be susceptible to interaction with study or other drugs, which may reduce the efficacy of the contraception method.

Abstinence (relative to heterosexual activity) can only be used as the sole method of contraception if it is consistently employed during the entire period of risk associated with the study treatments as the subject's preferred and usual lifestyle.

Periodic abstinence (e.g., calendar, ovulation, symptothermal, or postovulation methods) and withdrawal (coitus interruptus), spermicides only, and lactational amenorrhea method (LAM) are not acceptable methods of contraception. Female condom and male condom should not be used together as an effective method of contraception.

Subjects should be informed that taking the study drug may involve unknown risks to the fetus (unborn baby) if pregnancy were to occur during the study. To participate in the

study, subjects of childbearing potential must adhere to the contraception requirement (described above) from the day of study drug initiation (or 14 days prior to the initiation of study drug for oral contraception) throughout the study period up to 2 days after the last dose of acalabrutinib. If there is any question that a subject of childbearing potential will not reliably comply with the requirements for contraception, that subject should not be entered into the study.

Subjects should promptly notify the investigator if they become pregnant during this study or within 2 days after the last dose of acalabrutinib. If a woman becomes pregnant during the treatment period, she must discontinue acalabrutinib immediately. Pregnancy in a woman must be reported as outlined in [Section 6.2.4](#).

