	
first dose of acalabrutinib; MRI must have been obtained ≥ 4 weeks after any salvage surgery after first or second relapse.
 
5. Stable or decreasing dose of corticosteroids ≥ 5 days before baseline MRI (at study entry).6. On a stable dose of any required therapy (such as anticonvulsant medication for subjects to be enrolled into the Phase 1b portion), for ≥ 3 weeks before the first dose of acalabrutinib.7. Eastern Cooperative Oncology Group (ECOG) performance status of ≤ 2.8. Life expectancy ≥ 12 weeks.9. Completion of all prior anticancer therapy including investigational therapy ≥ 2 weeks before the first dose of acalabrutinib. Exceptions include: ≥ 6 weeks for nitrosoureas, ≥ 4 weeks for surgery, and ≥ 12 weeks for radiotherapy.10. Need to have recovered (i.e., Grade ≤ 1 or baseline) from AEs associated with prior cancer therapy. Note: Subjects with Grade ≤ 2 neuropathy or Grade ≤ 2 alopecia are an exception, and may qualify for the study.11. Women who are sexually active and can bear children must agree to use highly effective forms of contraception during the study and for 90 days after the last dose of acalabrutinib. Highly effective forms of contraception are defined in protocol.12. Men who are sexually active and can beget children must agree to use highly effective forms of contraception during the study and for 90 days after the last dose of acalabrutinib. Highly effective forms of contraception are defined in protocol.13. Men must agree to refrain from sperm donation during the study and for 90 days after the last dose of acalabrutinib.14. Note: This inclusion criterion no longer applies under Amendment 1 of the protocol.15. Willing and able to participate in all required evaluations and procedures in this study protocol, including swallowing capsules without difficulty.16. Ability to understand the purpose and risks of the study and provide signed and dated informed consent and authorization to use protected health information (in accordance with national and local patient privacy regulations). Note: If clinically indicated, an authorized legal representative may provide informed consent.
--	--

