11. Women who are sexually active and can bear children must agree to use highly effective forms of contraception during the study and for 90 days after the last dose of acalabrutinib. Highly effective forms of contraception are defined in [Section 3.9.8](#).
12. Men who are sexually active and can beget children must agree to use highly effective forms of contraception during the study and for 90 days after the last dose of acalabrutinib. Highly effective forms of contraception are defined in [Section 3.9.8](#).
13. Men must agree to refrain from sperm donation during the study and for 90 days after the last dose of acalabrutinib.
14. Note: This inclusion criterion no longer applies under Amendment 1 of the protocol.
15. Willing and able to participate in all required evaluations and procedures in this study protocol including swallowing capsules without difficulty.
16. Ability to understand the purpose and risks of the study and provide signed and dated informed consent and authorization to use protected health information (in accordance with national and local patient privacy regulations). Note: If clinically indicated, an authorized legal representative may provide informed consent.

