6.2.4 Pregnancy

The investigator should report all pregnancies of subjects within 24 hours using the Pregnancy Report Form. This form should be faxed or emailed to Acerta Pharma Drug Safety. Any pregnancy-associated SAE must be reported to Acerta Pharma, according to the usual timelines and directions for SAE reporting ([Section 6.2.5](#)).

Any uncomplicated pregnancy that occurs with the subject during this study will be reported. All pregnancies that are identified during or after this study, wherein the estimated date of conception is determined to have occurred from the time of consent to 90 days after the last dose of study medication will be reported, followed to conclusion, and the outcome reported.

A pregnancy itself is not regarded as an AE unless there is suspicion that the investigational product under study may have interfered with the effectiveness of a contraceptive medication. Likewise, elective abortions without complications are not considered AEs. Any SAEs associated with pregnancy (e.g., congenital abnormalities/birth defects/spontaneous miscarriage or any other serious events) must additionally be reported as such using the SAE report form.

Subjects should be instructed to immediately notify the investigator of any pregnancies. Any female subjects receiving study drug who become pregnant must immediately discontinue study drug. The investigator should counsel the subject, discussing any risks of continuing the pregnancy and any possible effects on the fetus.

Upon completion of the pregnancy, additional information on the mother, pregnancy, and baby will be collected and sent to ^{PPD} [REDACTED]

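### The inclusion criteria require contraception from women and men for 90 days after the last dose; Section 3.9.8 requires 2 days from women and none from men with a partner of childbearing potential

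*Protocol*

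**What the plan says.** The eligibility criteria are the same in the synopsis and in Protocol Section 3.3.1.

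- Criterion 11 applies to female subjects: "Women who are sexually active and can bear children must agree to use highly effective forms of contraception during the study and for 90 days". The period is counted from the final dose.
- Criterion 12 applies to male subjects: "Men who are sexually active and can beget children must agree to use highly effective forms of contraception during the study and for 90 days". The period is counted in the same way.
- Criterion 13: "Men must agree to refrain from sperm donation during the study and for 90 days after the last dose of acalabrutinib".

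In Section 3.3.1, criteria 11 and 12 point to Section 3.9.8 for the definition of highly effective methods; the synopsis points to the protocol in general.

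Section 3.9.8 requires contraception of women of childbearing potential during treatment "and for 2 days after the last dose of acalabrutinib". It later makes contraception a condition of taking part, "throughout the study period up to 2 days after the last dose of acalabrutinib". On men it says: "For male subjects with a pregnant or non-pregnant WOCBP partner, no contraception measures are required". It does not mention sperm donation.

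On pregnancy, Section 3.9.8 says: "Subjects should promptly notify the investigator if they become pregnant during this study or within 2 days after the last dose of acalabrutinib". Section 6.2.4 covers pregnancies with an estimated conception date "from the time of consent to 90 days after the last dose of study medication will be reported", and also has subjects told to report any pregnancy at once, with no time limit.

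**The concern.** Two operative parts of one protocol set different conditions of participation for the same people. A sexually active man who can father children, has a partner of childbearing potential and declines contraception fails criterion 12, yet Section 3.9.8 says nothing is required of him. A woman who agrees to 2 days satisfies the condition in Section 3.9.8 and fails criterion 11. Two sites could apply different eligibility and post-treatment rules, and each could cite the protocol in support.

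What is at stake is consistent eligibility, consistent instructions to subjects after treatment, and clear pregnancy notification.

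**Working it through.** No statistical figure is involved, so the check sets the current provisions side by side.

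| Item | Inclusion criteria (synopsis, 3.3.1) | Section 3.9.8 | Section 6.2.4 |
|---|---|---|---|
| Women, contraception after last dose | 90 days (criterion 11) | 2 days, stated twice | – |
| Men with a partner of childbearing potential | Required, 90 days (criterion 12) | Not required | – |
| Sperm donation | Barred, 90 days (criterion 13) | Not mentioned | – |
| Subject notifies a pregnancy | – | During study or within 2 days after last dose | Any pregnancy, at once |
| Conceptions to be reported | – | Refers to 6.2.4 | Up to 90 days after last dose |

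1. **Women.** 90 − 2 = 88 days between the two stated periods. This is a gap between rules, not an amount of lost data.
2. **Men.** Criterion 12 and the exemption in Section 3.9.8 cannot both describe the same sexually active man who can father children and has a partner of childbearing potential.
3. **Sperm donation.** Silence in Section 3.9.8 does not contradict criterion 13. The direct contradiction is with criteria 11 and 12. Criterion 13 belongs in the reconciliation because the position on men should be stated once.
4. **Pregnancy notification.** The sentence addressed to subjects in Section 3.9.8 is narrower than both provisions in Section 6.2.4.
5. **Is either text marked as superseded?** No. Elsewhere the protocol flags outdated rules with a note, as it does for criterion 14 and for the 400 mg QD cohort. Criteria 11 to 13 carry no such note. The visible list of updated sections at the front of the protocol includes 3.9.8 but neither 3.3.1 nor 6.2.4. That would fit an update that did not reach the other sections, although the documents do not state the cause.
6. **Reach.** SAP Section 3.2 and Table 1 give 15 subjects on 200 mg BID and 9 on 400 mg QD: 15 + 9 = 24. SAP Section 3.1 reports that the two committees did not recommend starting Phase 2. Protocol Sections 3.0 and 3.6 still allow subjects who benefit to continue treatment after the end of the study.

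**The case against.** The other side has several fair points.

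- **The cross-reference covers methods only.** Criteria 11 and 12 cite Section 3.9.8 to define acceptable contraception, and they state duration and coverage themselves. That is correct, but the conflict exists without the cross-reference, and a reader who follows it arrives at the contrary rule.
- **A site can satisfy both texts by applying the stricter one.** True. The protocol does not tell it to.
- **Section 3.9.8 hands pregnancy reporting to Section 6.2.4.** It does so directly after the 2-day sentence, and Section 6.2.4 has an open-ended instruction to subjects. A failure of notification is therefore not shown. What remains is an inconsistent instruction. A reporting window longer than a contraception window would not by itself be an error.
- **The eligibility consequence is largely hypothetical.** With 24 subjects enrolled and Phase 2 not recommended, prospective screening may be over. This narrows the practical reach. The protocol text still describes possible Phase 2 enrollment, and the post-dose rules apply to anyone still on treatment or within 90 days of the last dose. That number is not given and could be zero.

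These points limit the consequence. None removes the contradiction.

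**Conclusion.** The concern holds. Criteria 11 and 12 contradict Section 3.9.8 on the post-dose period for women (88 days apart) and on whether men with a partner of childbearing potential must use contraception at all. Criterion 13 has no counterpart in Section 3.9.8, and the notification sentence there is out of line with Section 6.2.4.

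The conclusion rests on the current protocol text alone and needs no assumption about which rule was intended. Three limits apply. No endpoint or analysis is affected. The consent form is not among the documents, so what subjects are actually told cannot be judged. The number of affected women of childbearing potential or sexually active men is not reported. This should be corrected, but it does not threaten the trial's results.

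**What to change.** Reconcile criteria 11 to 13, in the synopsis and Section 3.3.1, with Section 3.9.8, so that the protocol gives one post-dose contraception period and one statement on male subjects that also covers sperm donation. Align the notification sentence in Section 3.9.8 with the reporting window and the open-ended instruction in Section 6.2.4; Section 6.2.4 itself needs rewording only if the sponsor changes its window. Then check that the consent form matches.

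Which rule applies is for the sponsor's clinical and safety teams to decide; none is proposed here. The cost is a wording amendment and the consent-form check, with no added procedures, visits or patients.

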3.9.9 Overdose Instructions

Study drug overdose is the accidental or intentional use of the drug in an amount higher than the dose being studied. An overdose or incorrect administration of study drug is not an adverse event unless it results in untoward medical effects.

Any study drug overdose or incorrect administration of study drug should be noted on the Study Drug Administration eCRF.

All adverse events associated with an overdose or incorrect administration of study drug should be recorded on the Adverse Event eCRF. If the associated adverse event fulfills serious criteria, the event should be reported to the sponsor immediately (i.e., no more than 24 hours after learning of the event).

For any subject experiencing an acalabrutinib overdose, observation for any symptomatic side effects should be instituted, and vital signs, biochemical, and hematologic parameters should be followed closely (consistent with the protocol or more frequently, as needed). Appropriate supportive management to mitigate adverse effects should be initiated. If the overdose ingestion of acalabrutinib is recent and substantial, and if there are no medical contraindications, use of gastric lavage or induction of emesis may be considered.

3.10 WITHDRAWAL OF SUBJECTS FROM STUDY TREATMENT

The investigator, in consultation with the medical monitor, may withdraw any subject from study treatment, if, in the investigator's opinion, it is not in the subject's best interest to continue.

Any subject has the right to withdraw from the study treatment at any time. In addition, subjects may be withdrawn from study treatment for the following reasons:

- Progressive disease
- Start of alternative anticancer therapy
- Adverse event
- Pregnancy
- Investigator decision
- Subject's withdrawal of consent from study
- Decision by sponsor to terminate the study
- Subject lost to follow-up
- Death
- Other

Note: If the effects of ACP-196 stimulate an immune response in the tumor, it is possible that there could be pseudoprogression. If there is uncertainty regarding whether there is true cancer progression, the subject may continue study treatment and remain under close observation (e.g., evaluated at 4-week intervals) pending confirmation of progression. In particular, transient worsening of disease early in therapy or during temporary interruption of study therapy (e.g., for drug-related toxicity, surgery, or intercurrent illness) may not indicate cancer progression. In such circumstances, and if medically appropriate, subjects may resume therapy and relevant clinical, laboratory, and/or radiographic assessment can be attempted to document whether tumor control can be maintained or whether cancer progression has occurred.

Subjects who discontinue study treatment will continue to be followed on study for follow-up of safety ([Section 4.3](#)), disease progression, and survival unless they withdraw consent for further follow-up. Thus, all subjects receiving ≥ 1 dose of study drug will be followed during the immediate post-therapy and long-term follow-up assessments unless the subject withdraws consent for such follow-up to be conducted. The date the subject is withdrawn from study treatment or from the study (including long-term follow-up) and the reason for discontinuation will be recorded and also should be described on the appropriate eCRF.

3.11 REASONS FOR STUDY EXIT

Reasons for study exit include:

- Subject's withdrawal of consent from study
- Decision by sponsor to terminate the study
- Subject lost to follow-up
- Death

3.12 DATA AND SAFETY MONITORING

A Safety Review Committee will be formed as an internal monitoring committee to provide review and oversight of the safety/benefit-risk profile for the study. Additionally, a SAC will be formed with external advisors to provide guidance on protocol conduct and safety/benefit-risk profile for the study. Detailed information regarding the composition of the Safety Review Committee and SAC and detailed Safety Review Committee/SAC procedures will be provided in a separate charter. Adverse events and SAEs will be reviewed collaboratively by the Safety Review Committee and SAC after the first 24 subjects in the Phase 1b portion of the study, and on an ongoing basis (at least every 3 months), to identify safety concerns according to the charter. In addition, quarterly conference calls with the investigators and applicable site staff will be conducted to discuss study progress, obtain investigator feedback and exchange, and discuss "significant safety events" (i.e., AEs leading to dose reductions, related SAEs, and deaths).

4.0 STUDY ACTIVITIES AND ASSESSMENTS

The schedule of events is provided in [Appendix 1](#). Descriptions of the scheduled evaluations are outlined below and complete information on study drug and dosing is provided in [Section 3.4](#).

Before study entry, throughout the study, and at the follow-up evaluation, various clinical and diagnostic laboratory evaluations are outlined. The purpose of obtaining these detailed measurements is to ensure adequate safety and tolerability assessments. Clinical evaluations and laboratory studies may be repeated more frequently, if clinically indicated. This study will primarily use central laboratory testing for safety laboratory evaluations. Samples from sites' local laboratories will only be used if central laboratory testing is unavailable.

4.1 DESCRIPTION OF PROCEDURES

4.1.1 Informed Consent

The subject must read, understand and sign the ICF approved by the institutional review board or independent ethics committee (IRB/IEC), confirming his or her willingness to participate in this study before initiating any screening activity that is not considered standard of care by institutional standards. Subjects must also grant permission to use protected health information, if required by local regulations.

4.1.2 Medical History

Collect and record the subject's complete history through review of medical records and by interview. Concurrent medical signs and symptoms must be documented to establish baseline severities. A disease history, including the date of initial diagnosis and a list of all prior anticancer treatments, and responses and DOR to these treatments, also will be recorded.

4.1.3 Adverse Events

The accepted regulatory definition for an AE is provided in [Section 6.1](#). The AE reporting period is described in [Section 6.2.1](#). Important additional requirements for reporting SAEs are explained in [Section 6.2](#).

4.1.4 Concomitant Medications and Therapy

Document all concomitant medications and procedures that occur within 21 days before the start of study drug administration through 30 days after the last dose of study drug.

